## 7.6 Primary Endpoint Sensitivity Analysis

Acute Device Success will also be analyzed using a number of sensitivity analyses.

### 7.6.1 General Sensitivity Analyses

The rate of Acute Device Success will be analyzed based on the ITT and PP analysis sets.

### 7.6.2 FAS Sensitivity Analysis

To examine the effect of subjects for whom the *CSI Peripheral Guide Wire* was inserted but the OAD was not inserted, an analysis will be performed including the enrolled subjects that were not treated with OAD as having failed the primary endpoint.

### 7.6.3 Missing Data Sensitivity Analysis

A tipping point analysis will be performed on the mITT analysis set to assess outcomes in cases where the core lab is unable to assess outcomes due to missing or non-readable images. [REDACTED]

[REDACTED]

[REDACTED]

## 7.7 Secondary Endpoint Analyses

The following analyses will be presented on the analysis sets indicated.

### **7.7.1 Reduction in Lesion Stenosis**

Reduction in lesion stenosis presented as an absolute mean percentage change (defined as the difference between the pre-procedure measurement to both the value assessed post-OAD and the value post-OAD+POBA (and prior to DCB)) will be presented on a lesion level for the ITT and mITT analysis sets. Angiographic Core Lab values will be used in all cases.

### **7.7.2 Acute Technical Success**

Analysis of Acute Technical Success will be assessed post-procedure and performed on a subject level for the ITT and mITT analysis sets. Acute Technical Success is a composite endpoint comprised of:

- the number of subjects that have an Angiographic Core Lab assessed post-procedure (after all treatment is complete) residual stenosis of <30% if a stent has been used for any reason, and <50% if the subject was not stented and,
- no severe angiographic complications defined as severe dissections (D-F), perforation, or distal emboli requiring additional treatment during the procedure as adjudicated by the CEC

A subject is considered a success if both criteria are met.

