Clinically-driven target vessel revascularization (TVR)	A repeat procedure (percutaneous or surgical) performed for $\geq 50\%$ DS confirmed by angiography within all or part of the target vessel after documentation of recurrent clinical symptoms of PAD following the initial procedure.
Clinical Trial Treatment	Begins when OAS Guide Wire enters the body. Ends when the patient exits the Cath Lab.
De Novo Lesion	A native lesion not previously treated
Device Deficiency	
Inadequacy of a medical device with respect to its identity, quality, durability, reliability, usability, safety or performance
 
Note 1 to entry: Device deficiencies include malfunctions, use errors, and inadequacy in the information supplied by the manufacturer including labelling.
 
Note 2 to entry: This definition includes device deficiencies related to the investigational medical device or the comparator.
 
(per ISO 14155:2020)

Dissection classification	Type 0: None

Term	Definition															
	
Type A: Small radiolucent area within lumen of the vessel
 
Type B: Linear, non-persisting extravasation of contrast
 
Type C: Extraluminal, persisting extravasation of contrast
 
Type D: Spiral shaped filling defect
 
Type E: Persistent lumen defect with delayed ante/retrograde flow
 
Type F: Filling defect accompanied by total arterial occlusion
															
Enrolled Subjects	Subjects who met all of the Inclusion and none of the Exclusion criteria, signed an Institutional Review Board (IRB) approved ICF, and had the CSI Peripheral OAS Guide Wire enter the body.															
Enrolled and Treated Subjects	An Enrolled subject and the OAD enters the body.															
Inflow	
Arterial flow proximal to the protocol defined target area.
 
For this study, the iliac and common femoral are considered in-flow to the target area.
															

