8.2 Secondary Endpoints

The following secondary endpoints will be evaluated:

1. Reduction in lesion stenosis both post-OAD and post-OAD+POBA [Angiographic Core Lab assessed] (absolute mean percentage change defined as the difference between the pre-procedure percent stenosis and the percent stenosis measured post-OAD and post-OAD+POBA)
2. Acute technical success defined per the PARC definition of achievement of a final residual stenosis <30% for stented and <50% for non-stented subjects by angiography at the end of the procedure [Angiographic Core Lab assessed] without severe angiographic complications defined as severe dissections (D-F), perforation, or distal emboli requiring additional treatment during the procedure [CEC adjudicated]
3. DCB Device Success defined as the ability to achieve successful delivery and deployment of all DCB to the target lesion as described per the Instructions for Use (IFU) within 3 minutes of insertion without removal and use of an additional device.
4. Target vessel patency at 6 months defined as absence of clinically-driven Target Lesion Revascularization (TLR) and ≤2.4 peak systolic velocity ratio (PSVR) as assessed by Duplex Ultrasound [Duplex Ultrasound Core Lab assessed]. Clinically-driven TLR is defined as repeat procedure performed for ≥50% stenosis confirmed by angiography within all or part of the target lesion after documentation of recurrent clinical symptoms of PAD following clinical trial treatment [CEC adjudicated]
5. Rate of severe angiographic complications defined as severe dissections (D-F), perforation, or distal emboli requiring additional treatment during the procedure [CEC adjudicated]
6. Acute procedure success defined as both acute technical success and absence of death, stroke, MI, acute onset of limb ischemia, index bypass graft or treated segment thrombosis, and/or need for urgent/emergent vascular surgery within 72 hours of the clinical trial treatment [CEC adjudicated]
7. Major Adverse Event (MAE) rate at 30 days and 6 months [CEC adjudicated] defined as:

- a) All-cause death through 30 days **or**
- b) Major amputation of the target limb **or**
- c) Clinically-driven TLR

8. Adverse Event rates at 30 days and 6 months [CEC adjudicated]
9. Distribution of Rutherford Classification compared to baseline at 30 days and 6 months
10. Change in Ankle Brachial Index (ABI) after clinical trial treatment compared to baseline

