11.5 Before Clinical Trial Treatment

- **NON-TARGET LIMB** Non-target limb treatment must occur either greater than 30 days prior to the clinical trial treatment or greater than 30 days after the clinical trial treatment in the study according to **Section 12.4**.
- **INFLOW LESIONS IN THE TARGET LIMB** Inflow lesions (ipsilateral iliac and/or common femoral artery) in the target limb may be treated on the same day as the clinical trial treatment provided.
 - The inflow lesion must be successfully treated defined as residual stenosis \leq 50% without complications prior to insertion of the OAS guidewire in the target lesion to be revascularized. - **Refer to Clinical Trial Treatment Exclusion Criteria 31.**
 - The inflow lesion may only be treated with POBA or stenting.
 - Atherectomy, laser, other debulking devices, CTO devices, cutting balloons, scoring balloons, specialty balloons or similar devices cannot be used for the inflow treatment. - **Refer to Clinical Trial Treatment Exclusion Criteria 38.**
- **NON-INFLOW, NON-TARGET LESIONS IN THE TARGET LIMB**
 - Treatment of lesion(s) not considered Inflow or Target Lesion cannot occur on the day of the clinical trial treatment.
 - Non-target lesion treatment on the target limb must occur greater than 30 days after the clinical trial treatment in the study. - **Refer to General Exclusion Criteria 8 and 10.**
- Access artery by operator's preferred methodology for target limb treatment.

- Cross the lesion using the operator's preferred wire (CSI Peripheral OAS Guide Wire cannot be used at this point).
- Assess Clinical Trial Treatment Inclusion/Exclusion criteria including Calcium Assessment using IVUS and/or angiography – **Refer to Appendix A** to determine when IVUS and angiography images are taken.
 - IVUS Catheter – refer to IVUS IFU to determine appropriate IVUS catheter size.
 - One pass of the IVUS Catheter will be attempted in order to perform Calcium Assessment. If IVUS cannot cross the lesion, do not attempt crossing with IVUS again.
 - Ensure angiographic images have been collected.
 - To complete the Calcium Assessment, **Refer to Appendix B** to determine how to use data from IVUS and/or angiography to determine Calcium Assessment.
- Based on feedback from physician experts, there are no differences in patient characteristics that impact outcomes if calcium is measured by IVUS or angiography.
- Refer to **Figure 1** for the defined treatment area.

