### **7.7.6 Acute Procedure Success**

Acute Procedure Success will be assessed 72 hours after the index procedure and presented on the mITT and FAS. Acute Procedure Success is defined as Acute Technical Success and absence of: death by any cause, stroke, MI, acute onset of limb ischemia, index bypass graft or segment thrombosis, and/or need for urgent/emergent vascular surgery within 72 hours of the clinical trial treatment as adjudicated by the CEC.

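### Acute technical success: the stricter <30% limit is triggered by a stent anywhere in the subject, so a permitted same-day inflow stent could fail an unstented target lesion

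*SAP*

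**What the plan says.** SAP 7.7.2 defines acute technical success as a composite, "performed on a subject level for the ITT and mITT analysis sets". Its angiographic component is a core-lab value taken once all treatment is finished: "residual stenosis of <30% if a stent has been used for any reason, and <50% if the subject was not stented". The second component is freedom from severe angiographic complications.

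Protocol 8.2 words the same endpoint as "final residual stenosis <30% for stented and <50% for non-stented subjects by angiography at the end of the procedure". It too classifies the subject, not the lesion, as stented or not. The phrase about any reason appears only in the SAP.

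Protocol 11.5 says that inflow lesions "in the target limb may be treated on the same day as the clinical trial treatment", and that "The inflow lesion may only be treated with POBA or stenting". The protocol definitions place these vessels outside the target area: "For this study, the iliac and common femoral are considered in-flow to the target area".

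SAP 7.7.6 builds on the endpoint: "Acute Procedure Success is defined as Acute Technical Success and absence of: death by any cause, stroke, MI", followed by further events within 72 hours.

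**The concern.** The stent switch decides which of two residual-stenosis limits a subject must meet. As written, it asks whether the subject received a stent, without saying where. The protocol allows a stent in a different vessel on the same day, so the limit applied to the target lesion can depend on treatment of inflow disease.

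Two success rates are at stake: acute technical success and acute procedure success. If inflow stents count, both rates vary with how often sites treat inflow disease at the same session, which has nothing to do with the study device. If one programmer counts them and another does not, the same data give two different rates. A pre-specified definition is meant to prevent that.

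**Working it through.** **The plan's own figure.** No expected rate is stated for acute technical success. The only design figure is the sample size for the primary endpoint, used here as the denominator. With anticipated rate 0.70, performance goal 0.50, one-sided alpha 0.025 and power 0.90 (Protocol 9.1.5, SAP 3.5):

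n = [1.960 × √(0.5 × 0.5) + 1.282 × √(0.7 × 0.3)]² / (0.70 − 0.50)² = 61.4, rounded up to 62.

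The figure reproduces. The point does not depend on it.

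**Can an inflow-stented subject reach the analysis?** Yes. Clinical Trial Treatment Exclusion 31 removes only inflow treatment that was unsuccessful or complicated. A successfully stented inflow lesion does not exclude the subject.

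**Which subjects change status?** Take subjects with no severe angiographic complication and compare two readings of the switch.

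| Inflow stent | Target-lesion stent | Final target-lesion stenosis | Any stent sets the limit | Only a target-lesion stent sets the limit |
|---|---|---|---|---|
| No | No | 30% to <50% | Pass | Pass |
| Yes | No | below 30% | Pass | Pass |
| Yes | No | 30% to <50% | **Fail** | **Pass** |
| Yes | No | 50% or more | Fail | Fail |
| Yes or no | Yes | 30% to <50% | Fail | Fail |

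Only the third row differs. For example, an iliac stent plus an unstented superficial femoral lesion ending at 40% fails on one reading and passes on the other. The first row, with the same target-lesion result and no inflow stent, passes on both. The difference runs one way: counting inflow stents can only lower the rate.

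**How many subjects?** Let s be the share of subjects with an inflow stent, and q the share of those whose unstented target lesion ends at 30% to <50%. The share changing status is at most s × q, and the count is 62 × s × q. The documents give neither s nor q, so both ranges are assumptions.

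| s | q = 10% | q = 25% | q = 40% |
|---|---|---|---|
| 5% | 0.31 | 0.78 | 1.24 |
| 10% | 0.62 | 1.55 | 2.48 |
| 20% | 1.24 | 3.10 | 4.96 |
| 30% | 1.86 | 4.65 | 7.44 |

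The extremes are 62 × 0.05 × 0.10 = 0.31 (0.5% of subjects) and 62 × 0.30 × 0.40 = 7.44 (12%). Subjects who fail anyway through a severe complication would not change status, so each count is an upper value for its s and q.

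**The case against.** There is a good case that the narrower reading is intended.

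- SAP 6.5 says that subject-level endpoints have their success and failure criteria judged on target lesions. SAP 7.7.2 does not attach the residual stenosis to the target lesion either, yet nobody would measure it in the iliac artery. The same context can be supplied for the stent.
- The phrase about any reason most naturally concerns why a stent was placed (bail-out, dissection, recoil), not where.
- Clinical Trial Treatment starts when the OAS guide wire enters the body. Inflow treatment must be complete "without complications prior to insertion of the OAS guidewire in the target lesion to be revascularized", so an inflow stent falls before the defined treatment period.
- The body of SAP 6.2 (Analysis Conventions) is redacted and the CRFs are not available. Either may settle the matter.

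Most of this stands, and it makes a target-lesion reading the more likely intention. But none of the visible text says which stents set the limit. SAP 6.5 says which lesions are judged. SAP 7.7.2 does not limit the stent to the Clinical Trial Treatment period, and the visible text does not define the procedure. Neighbouring sections do name the target lesion where they mean it: DCB delivery in SAP 7.7.3 and repeat procedures in SAP 7.7.4. Section 7.7.2 does not.

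A reader might infer that the SAP intends inflow stents to count, so that subjects will be wrongly failed. The documents do not support that; misclassification follows only if the sentence is programmed literally. A reader might also settle on a central effect, such as 3 to 8 percentage points from assuming s of 10–20% and q of 30–40%. Nothing in the documents favours those values over lower ones, and under the wider range the effect may be less than one subject.

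**Conclusion.** The point holds as a defect of wording. Applied as written, the SAP 7.7.2 rule can fail an unstented target lesion at 30% to <50% because of a permitted stent in another vessel. Acute procedure success inherits the result. The surrounding text leans towards counting target-lesion stents only but does not say so.

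The size is not estimable from the documents. The range of 0.3 to 7.4 of 62 rests entirely on the assumed 5–30% and 10–40%.

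The consequences are limited. Protocol 25.4.3 attaches no formal hypothesis test to secondary endpoints. Any error would understate the reported rates, so it could not flatter the device. It would be wrong to infer that the trial's success criterion is touched: acute device success has a single limit of 50% or less, assessed after OAD and POBA, with no stent condition.

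**What to change.** In SAP 7.7.2, replace the stent condition with wording such as: *<30% if a stent was placed in the target lesion (as identified in Section 6.5), whatever the indication; <50% if no stent was placed in the target lesion; inflow or other non-target stents do not change the limit.* Bail-out stents in the target lesion stay under the stricter limit.

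Use the same derivation for SAP 7.7.6, and state in the SAP that the stented/non-stented split in Protocol 8.2 and in the protocol definitions is read the same way. Confirm that the CRF records the location of each stent; this could not be checked here. If the sponsor does intend any stent to count, the SAP should say so and give the reason.

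The cost is one sentence and a derivation by stent location, with no change to study conduct. If stent location is not recorded, it would have to be obtained from procedure records or the angiograms.

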### **7.7.3 DCB Device Success**

DCB Device success will be assessed on the ITT and mITT analysis sets. DCB device success will be assessed on a subject level and is defined as successful delivery and deployment of all DCB to the target lesion. Successful delivery must be performed per the Instructions for Use (IFU); deployment of each DCB must occur within 3 minutes of insertion. Removal of a DCB and use of any non-DCB therapy prior to delivery of a subsequent DCB or use of any adjunctive therapy (including stents) after DCB will be counted as a failure. DCB Device success is based on investigator reported data.

### **7.7.4 Target Vessel Patency**

The rate of Target Vessel Patency will be presented on a lesion level for ITT and mITT analysis sets at the time-point of 6 months on subjects with a 6-month visit. Target Vessel Patency is a binary composite endpoint comprised of:

- CEC adjudicated absence of clinically driven repeat procedure performed for  $\geq 50\%$  stenosis confirmed by angiography within all or part of the target lesion after documentation of recurrent clinical symptoms of PAD following clinical trial treatment procedure (i.e. clinically-driven TLR) occurring at any time-point on, or prior to the 6-month visit date and,

- a Duplex Ultrasound Core Lab assessed PSVR value of  $\leq 2.4$  (or equivalent by visual assessment if the lesion is non-patent and the PSVR cannot be numerically calculated).

The vessel is considered patent if both criteria are met at the time of assessment.

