14. FOLLOW-UP

The following sections describe follow-up requirements for all enrolled subjects in the KAIZEN study. All follow-up assessments and visits must be performed by someone who is study-trained and delegated to perform study follow-up.

- If the subject is seen by the Investigator between scheduled follow-up visits (i.e., not a study required assessment or visit), the assessment/visit should not be recorded on an CRF. However, if any adverse events are noted, an Adverse Event (AE) CRF needs to be completed for each event.
- If a revascularization occurs, images are required to be submitted for CEC review. The subject will still be required to return for the next scheduled follow-up visit if the unscheduled visit is out of the compliance follow-up window.

14.1 30-Day In-hospital Follow-up Visit or Telephone Follow-up Assessment

All Enrolled / Enrolled and Treated subjects are required to have a follow-up assessment occur at 30 days (+14 days) after enrollment. The 30-Day assessment can be an in-hospital follow-up visit or may occur by telephone assessment.

Refer to **Table 7** for 30-Day In-hospital Follow-up Visit or Telephone Follow-up Assessment data collection requirements.

14.2 6-Month Follow-up Visit

All Enrolled subjects are required to have a 6-Month (+30 days) Follow-up assessment phone call or in-hospital visit to monitor for adverse events.

All Enrolled and Treated subjects are required to have a Follow-up assessment occur at 6-Months (+30 days) after clinical trial treatment. The 6-Month visit must be an in-hospital visit.

Refer to **Table 7** for 6-Month Follow-up Visit data collection requirements.

All subjects will be exited from the study following the 6-month Follow-up visit.

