16.4 Reporting Adverse Events and Follow-Up

Adverse events should be reported throughout the subject's participation in the trial and not only at study mandated visits. Any subject who has unresolved adverse events at the end of their study participation will continue to be followed by the investigator per their standard of care. Source documents should be submitted to the Sponsor for review of the Adverse Event. Prior to submission to the Sponsor the source documents are to be appropriately redacted to remove the subject's name, and any other identifying information and the subjects unique Subject ID should be inserted on every page.

All adverse events, including subject deaths, must be reported on the AE CRF. In the event an adverse event cannot be submitted through the electronic database in a timely fashion, submission may be made to the Sponsor via email to [REDACTED] This does not replace the EDC reporting system; however, all information must still be entered in the EDC system as soon as feasible.

All efforts should be made to notify the Sponsor as soon as possible after first learning of an SAE. Additional information, obtained after the initial SAE, must also be reported as soon as possible to the study Sponsor. Deaths must be reported on the Study Exit CRF. If available, a copy of death records, medical records for the events that led to the subject's death, death

certificate and an autopsy report must be sent to the Sponsor as soon as they become available. Adverse event information will be collected up until each subject's study exit or study completion.

All AEs will be reviewed by the Sponsor and determined whether the AE meets regulatory reporting requirements. These events will be reported to the country's regulatory authorities according to the requirements of the country by the Sponsor or designee. The Investigator is responsible for reporting to the IRB, as applicable. In cases where the CEC does not agree with the Investigator's final assessment/classification of an adverse event, the Sponsor shall communicate both opinions to the regulatory authorities, if applicable.

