## 6.4 Analysis Windows

Assessments will be made at baseline ( $\leq$  30 days prior to procedure), during the procedure, and post-procedure/discharge. Follow-up visits (analysis windows) are scheduled as office visits or phone call at the following time points post-procedure: 30-days (+14 days) and 6-months (+30 days). All windows will be calculated in days (i.e. 6-months will be calculated as 180 days).

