### 7.1 Subject Disposition

Subject disposition data will be presented on the FAS set unless otherwise noted. Tabulated data will be provided for:

The number of subjects enrolled at each site that fall into each analysis set (e.g., FAS, ITT, mITT)

Compliance to the follow-up visit schedule for subjects in the FAS and mITT analysis sets

The number and percentage of subjects by discontinuation reason

The listing of reasons will be provided for subjects excluded from the mITT and PP analysis set

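### SAP 7.7.4 computes 6-month patency only in subjects with a 6-month visit, so an adjudicated clinically-driven TLR without such a visit drops out although it already establishes failure (small effect, cheap to repair)

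*SAP*

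**What the plan says.** - **Denominator.** SAP 7.7.4 gives patency as a binary lesion-level rate in the ITT and mITT sets, "at the time-point of 6 months on subjects with a 6-month visit".
- **TLR component.** It counts CEC-adjudicated clinically-driven TLR "occurring at any time-point on, or prior to the 6-month visit date". The vessel is patent only if the TLR and PSVR criteria are both met.
- **Protocol definition.** Protocol 8.2 uses the same two components at 6 months. It does not itself restrict the rate to attenders, although Protocol Table 7 schedules duplex only at the 6-month visit.
- **After a revascularization.** Protocol 14 says "The subject will still be required to return for the next scheduled follow-up visit", on the condition that the unscheduled visit was outside the follow-up window. An in-window revascularization visit may therefore serve as the scheduled one.
- **End of follow-up.** Protocol 14.2 says "All subjects will be exited from the study following the 6-month Follow-up visit". Protocol 16.4 adds "Adverse event information will be collected up until each subject's study exit or study completion". The visit window is +30 days only, and SAP 6.4 counts six months as 180 days.
- **Other uses of TLR.** SAP 7.7.7 uses clinically-driven TLR in the MAE time-to-event analysis, read at day 210 for 6 months, and permits but does not require component rates.
- **Missing data.** The tipping-point analysis in SAP 7.6.3 belongs to the primary endpoint. The text of SAP 6.2 and the list in SAP 6.3 are not visible.

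**The concern.** A subject with an adjudicated TLR is a known patency failure, not a missing value. Protocol 18 lists death, withdrawal and loss to follow-up as reasons for exit, and any of them can follow a TLR. Under SAP 7.7.4 such a subject has no 6-month visit and is removed from the calculation.

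If TLR subjects miss the visit more often than others, the reported rate is too high; if they miss it less often, too low. A reader could trace an absent TLR subject through the table of "Compliance to the follow-up visit schedule for subjects in the FAS and mITT analysis sets" (SAP 7.1) and the MAE and AE outputs, but could not see the effect on patency. At stake is the only duplex-based 6-month effectiveness measure in a study meant to support commercialization in Japan.

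**Working it through.** The plan states no patency, TLR, PSVR-failure or attrition rate, so there is no figure of its own to reproduce. N = 62 (SAP 3.5) serves only as an illustrative denominator. All rates below are assumptions.

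**1. Closed form.** Let t be the proportion with TLR, v = 14% the proportion failing on PSVR only, P = 1 - t - v true patency, aT the share of TLR subjects without a visit, and aO = 10% the share of the others. One lesion per subject, every TLR observed.

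SAP rate = P(1 - aO) / [(1 - t)(1 - aO) + t(1 - aT)]

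| t | True P | aT | Calculation | SAP rate | Error (points) |
|---|---|---|---|---|---|
| 10% | 76.0% | 0% | 0.684/0.910 | 75.2% | -0.8 |
| 10% | 76.0% | 10% | 0.684/0.900 | 76.0% | 0 |
| 10% | 76.0% | 20% | 0.684/0.890 | 76.9% | +0.9 |
| 10% | 76.0% | 30% | 0.684/0.880 | 77.7% | +1.7 |
| 3% | 83.0% | 20% | 0.747/0.897 | 83.3% | +0.3 |
| 3% | 83.0% | 30% | 0.747/0.894 | 83.6% | +0.6 |

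With 62 × 0.9 = 55.8 attenders, the sampling SD is √(0.76 × 0.24/55.8) = 5.7 points, or √(0.83 × 0.17/55.8) = 5.0 points. At aT = 20% the expected number of known failures dropped is 62 × 0.03 × 0.20 = 0.4 to 62 × 0.10 × 0.20 = 1.2, and fewer if some subjects leave before their TLR occurs.

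**2. An estimate that uses every TLR.** Multiply freedom from TLR by the proportion patent among TLR-free attenders: 0.90 × 0.684/0.810 = 76.0%, whatever aT is.

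**3. Simply adding the known failures back.** If every TLR is observed, this gives 0.684/0.910 = 75.2%, which is 0.8 points low. If 10% drop out evenly over 180 days and the TLR hazard is constant (10% by day 180), the mean chance that a dropout's TLR comes first is 1 - 0.1/(-ln 0.9) = 5.1%. The proportion is then 0.684/(0.900 + 0.1 × 0.051) = 75.6%, about 0.4 points low. The shortfall depends on when people leave.

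**4. Worked example, 62 subjects.** Take 44 patent, 8 PSVR failures, 6 TLRs and 4 TLR-free non-attenders, with one TLR subject absent (1/6 = 17%, against 4/56 = 7% of the others).

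- SAP rate: 44/(44 + 8 + 5) = 44/57 = 77.2%.
- Product estimate: the duplex factor is 44/52. Kaplan-Meier freedom from TLR lies between 1 - 6/58 and 1 - 6/62, according to whether the 4 leave before the first or after the last TLR. The product is 75.9% to 76.4%.
- Bounds with known TLRs kept as failures: 44/62 = 71.0% and 48/62 = 77.4%.

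**5. Simulation.** N = 62, 12,000 runs, 10% TLR by day 180 at constant hazard, visits spread evenly over days 180-210, 10% unrelated dropout, PSVR failure in 15.6% of TLR-free subjects. True patency at the visit is 75.4%. With 0/11/22% extra loss after TLR:

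- SAP rate: 75.4/76.3/77.3%.
- Product with Kaplan-Meier at day 180: 75.4/75.5/75.5% (SD 5.7-5.8).
- Product with Kaplan-Meier at day 210: 74.7% throughout (SD 6.2-6.4), because most attenders have already left the risk set.

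**The case against.** **The case for leaving the text alone.** The rate is unbiased when attrition is unrelated to outcome, and nothing in the documents says TLR subjects miss visits more often. Protocol 14 asks revascularized subjects to return, and Protocol 18 requires at least three contact attempts and a traceable letter before a subject is called lost. SAP 7.7.7 already uses the TLR without a visit condition and may show it as a component. In the example the SAP figure lies inside the bounds. All of this stands and keeps the point small. It does not close the gap: contact efforts cannot prevent death or withdrawal, and a TLR component rate is not a patency estimate.

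**Stronger readings that a reader might infer, and that the documents do not support:**

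- *Patency is necessarily overstated.* The error is negative when TLR subjects attend better than others, and no known failure is dropped if all attend.
- *The plan has no rule for this case.* SAP 6.2 and 6.3 are not visible, so only the visible text can be called silent.
- *The SAP contradicts the protocol definition.* Classifying a vessel as patent needs a duplex, which is scheduled only at the 6-month visit. The narrower point is that classifying it as failed after a TLR does not.
- *The distortion is several points.* That needs, for instance, five absent TLR subjects while all 57 others attend, for which the documents give no ground.

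**Conclusion.** The point holds in limited form: an adjudicated TLR without a 6-month visit is removed by the denominator rule although the outcome is known, and nothing visible restores it for patency. The error of about -0.8 to +1.7 points rests on assumed TLR of 3-10%, PSVR failure of 14%, 10% attrition in TLR-free subjects and 0-30% in TLR subjects. Protocol 25.4.3 attaches no hypothesis test to secondary endpoints, so the primary conclusion and N = 62 are untouched. This is a worthwhile improvement at low cost, held with medium confidence because of the text that cannot be seen.

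**What to change.** Keep the attender rate in SAP 7.7.4 and add one supplementary estimate in which every adjudicated clinically-driven TLR counts as loss of patency, whether or not a visit occurred.

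- **Example.** Kaplan-Meier freedom from clinically-driven TLR at day 180, censored at death or study exit, times the proportion patent at the visit among attenders who were TLR-free at day 180 and have an evaluable outcome. Patent means no TLR after day 180 up to the visit and PSVR at most 2.4. Day 180 suits the one-sided window, since no subject with an in-window visit has exited before then.
- **State** the unit (lesion level as in 7.7.4, or subject level) and how visits before day 180 are handled.
- **Report beside it** the number of TLR subjects without a visit, the number of TLR-free subjects without an evaluable duplex, and best/worst-case bounds with known TLRs kept as failures. The product assumes that TLR-free subjects with and without duplex are alike; the bounds show the effect if they are not.
- **If a simple proportion keeping known failures is also shown,** say that it tends to lean low by an amount that depends on attrition, and do not quote a fixed figure.
- **If SAP 6.2 or 6.3 already holds such a rule,** a cross-reference in 7.7.4 is enough.

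The cost is a few sentences and one table, from TLR dates, exit dates and duplex results already collected. The downside is a second patency figure that must be labelled clearly.
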